AND with postmenopausal gonadotropin levels (luteinizing hormone and follicle-stimulating hormone levels at least 40 IU/L) or postmenopausal estradiol level (less than 5 ng/dL) or according to the definition of "postmenopausal range" for the laboratory involved.

OR

- Underwent bilateral oophorectomy OR
- Underwent hysterectomy OR
- Underwent bilateral salpingectomy

- Currently receiving treatment in another drug study or an investigational device study, or less than 90 days prior to screening since ending treatment on another investigational device or drug study(-ies)
- Has received CGRP monoclonal antibody within 4 months of the start of the run-in phase
- Active chronic pain condition that in the investigator's opinion is unrelated to migraine (e.g. chronic pelvic pain)
- Acute pain condition that in the investigator's opinion is unrelated to migraine (e.g. post-surgical pain)
- Unable to provide informed consent
- Less than 80% compliance with providing headache diary data during the run-in phase (i.e. provides data on less than 80% of days)

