#### Daily Headache Diary

A daily headache diary will be completed for the next 12 weeks to allow for assessment of changes in headache and migraine frequency. Headache diary data will be analyzed to classify patients as “responders” (50% or greater reduction in migraine day frequency between weeks 5-8 post first erenumab treatment compared to frequency during the run-in phase) or “non-responders” (less than 50% reduction in migraine day frequency during weeks 5-8 post first erenumab treatment compared to the frequency during the run-in phase). Since patient outcome will be measured at 8 weeks (opposed to 12 weeks like is done in the majority of clinical trials), depending upon patient outcomes other definitions of “response” and “non-response” could be used. Furthermore, correlations between changes in migraine frequency and imaging outcomes could also be assessed.

A migraine day will be defined as follows: any calendar day during which a person experiences a qualified migraine headache (onset, continuation, or recurrence of the migraine headache). A qualified migraine headache is defined as a migraine with or without aura, lasting for at least 30 minutes, and meeting at least one of the following criteria (a and/or b):

- a) At least 2 of the following pain features: unilateral, throbbing, moderate to severe, exacerbated with exercise/physical activity
- b) At least 1 of the following associated symptoms: nausea and/or vomiting, photophobia and phonophobia

If the participant takes a migraine-specific medication (i.e. triptan or ergotamine) during aura or to treat headache on a calendar day, then it will be counted as a migraine day regardless of the duration and pain features/associated symptoms.

Missing values may exist in headache dairy data due to various reasons such as subjects’ missed recording, early withdrawal, or inadequate entries prohibiting evaluation of the end point (responder vs. non-responder). To impute the missing data and allow for evaluation of migraine frequency,

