classic imputation methods commonly used in clinical trials will be adopted.(6) Specifically, for months with 20-27 days of dairy data, the values for missing entries will be imputed by prorating scores of 28-day post-treatment periods. That is, monthly migraine frequency can be calculated as the ratio of number of observed migraine days to number of observed days multiplied by 28. For months with less than 10 days of dairy data, monthly migraine frequency will be estimated by the substitution of the patient's previous 28-day period score, multiplied by the ratio of the mean for all patients in the same period to the mean for all patients in the previous period. For post-treatment periods with 10-19 days of diary data, scores will be estimated using a mean of both methods.

**Follow up visits One through Four (see table 1):** Four follow-up visits will be scheduled: at weeks 2, 4, 8 and 12 post-initial treatment with erenumab (week 2 = 14 days +/- 2 days since first visit; week 4 = 28 days +3 days since first visit; week 8 = 56 days +/- 3 days since first visit; week 12 = 84 days +/- 5 days since first visit). The early follow-up at 2 weeks will be utilized for repeat QST, brain imaging and cognitive testing so that data are available for investigating early markers/predictors of treatment response. A second treatment with erenumab will occur during the 4-week visit. Imaging, QST and neurocognitive testing will be repeated during the 8-week visit, allowing for determination of biomarkers for treatment response that might not have been found at the early time-point of 2 weeks and that can be correlated with clinical measures of treatment response (i.e. changes in migraine day frequency). The 12-week visit will allow for further assessment of safety and efficacy.

**Acute Migraine Therapy:** Patients will be allowed to use acute headache treatments including migraine-specific medication (e.g. triptans, ergotamine derivatives) and NSAIDs during the study.

**Other Migraine Preventive Therapy:** Patients will be allowed to use two or fewer migraine preventive therapies in addition to erenumab as long as the dose has been stable for at least 2 months before the start of the run-in phase. Changes to the dose of such treatments will not be allowed during this study unless necessary due to safety issues or lack of tolerability.

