*Specific Aim #2 (i.e. Develop models to predict which patients will respond to erenumab):* Pre-treatment scans will be used to identify MRI predictors of erenumab response. Multivariate machine-learning modeling of brain structural and functional data will be utilized for developing the predictive model. Because there are many imaging features available, but only a limited set of patients for this analysis, principal components analysis (PCA) will be performed on features collected from each imaging type to reduce the dimensionality of the data. The principal components (PCs) that result from PCA are linear combinations of the original imaging features, and can consolidate the information from the original features in such a way that only a few PCs are needed to explain most of the data variance. PCA will be performed separately on features from each imaging type to enhance clinical interpretability of PCs chosen for the predictive model.

To maximize the prediction accuracy, we will employ an ensemble learning approach by including a number of contemporary and complementary machine learning algorithms for building the predictive model, including Linear Discriminant Analysis (LDA), Quadratic Discriminant Analysis (QDA), Support Vector Machines (SVM), and Decision Tree (DT). Integrating these algorithms with Particle Swarm

Optimization (PSO)-based feature selection, we will identify the subset of features (PCs) that maximizes cross-validated accuracy of predicting responders and non-responders. Feature selection is a key step to avoid overfitting when building a predictive model with limited samples. PSO is a bio-inspired optimization algorithm that mimics the collective and collaborative behavior of social swarms in nature, e.g., colonies, honeybees, and bird flocks, in finding the optimal feature subset, and has been shown to outperform conventional feature selection algorithms in numerous recent publications.

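### Patients with fewer than 10 diary days in both post-dose months all receive one shared imputed responder label, and nothing keeps that label out of the Aim 2 classifier

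*Combined protocol and SAP*

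**What the plan says.** **Responder definition.** The Daily Headache Diary section defines a responder by a "50% or greater reduction in migraine day frequency between weeks 5-8 post first erenumab treatment compared to frequency during the run-in phase".

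**Imputation.** The same section lists the causes of missing diary data that it means to cover, among them "early withdrawal, or inadequate entries prohibiting evaluation of the end point", and names that end point as responder versus non-responder. It gives three rules by number of diary days in a 28-day period:

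- 20-27 days: prorate the observed days to 28.
- 10-19 days: average the prorated score and the cohort-ratio score.
- "For months with less than 10 days of dairy data": the patient's own result from the period before is carried over and then "multiplied by the ratio of the mean for all patients in the same period to the mean for all patients in the previous period".

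**Run-in diary.** The Exclusion Criteria remove anyone with "Less than 80% compliance with providing headache diary data during the run-in phase", so every treated patient has a run-in score from which the rule can start.

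**Use of the label.** Under Specific Aim #2 in the Analysis Plans, "Pre-treatment scans will be used to identify MRI predictors of erenumab response". Features are then selected for cross-validated accuracy in separating responders from non-responders. The Informed Consent section keeps data collected up to withdrawal. The Analysis Plans set no minimum of post-dose diary for a label, do not exclude imputed labels, and name no sensitivity analysis for them.

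**The concern.** Carrying a patient forward at the cohort's rate of change is a tolerable way to fill in a mean. It is a poor way to make a yes/no label for one patient. If nothing usable was recorded after the first dose, the label says only on which side of 50% the cohort's mean reduction fell. A patient who left within days because of an adverse event is then called a responder or a non-responder for reasons unrelated to that patient.

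Aim 2 is where this matters. The label is the target the classifiers learn, the quantity that feature selection optimises and the standard against which accuracy is scored. A patient who withdraws soon after dosing already has the baseline scan, so the lack of later scans does not keep that patient out of the pre-treatment model.

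**Working it through.** **The plan's own figures.** The plan states no figure for the imputation. The nearest are in Sample Size. 50 × 0.85 = 42.5, which gives the stated 21 + 21. The stated 88% power is also returned: a two-sample t test with 21 per group, difference 0.1, SD 0.1 and two-sided 0.05 gives 88.5%. Power plays no further part here.

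**Algebra.** Let B be the patient's run-in score and M0, M1, M2 the cohort means for run-in, weeks 1-4 and weeks 5-8. With fewer than 10 diary days in both post-dose months:

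- weeks 1-4 score = B × M1/M0
- weeks 5-8 score = (B × M1/M0) × (M2/M1) = B × M2/M0
- percent change = (B × M2/M0)/B − 1 = M2/M0 − 1

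B cancels, and up to 9 observed days in each month (18 in all) play no part in the patient's own score. The label is responder for all such patients if M2/M0 ≤ 0.5, and non-responder for all otherwise. The value is the percent change in cohort means, not the mean of individual percent changes.

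The text does not spell out the chaining, but without it the rule gives these patients no weeks 5-8 score. If the two ratios were computed on different sets of patients, M1 would not cancel exactly. The multiplier would still be one constant, so the label would still be shared.

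**Numerical check (simulated, assumed inputs).** 50 patients, run-in scores 6-25, 8 without post-dose diary, individual ratios of weeks 5-8 to run-in with SD 0.30:

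| Mean ratio set | Change given to all 8 | True responders among the 8 |
|---|---|---|
| 0.42 | −57.7% | 6 |
| 0.50 | −53.9% | 3 |
| 0.58 | −45.4% | 4 |

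Taking the run-in mean over completers only moved the common value by about 1 point. It stayed common.

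**How often the label is right.** If a fraction p of these patients are true responders, a shared responder label is right for p of them and a shared non-responder label for 1 − p. At the plan's p of about 50%, both are about half. This needs no simulation.

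**Which way the label falls.** The documents give no between-patient SD for the ratio, so a range is shown: 42 completers, run-in uniform on 6-25, ratios normal with the stated mean and SD before truncation at zero, 20,000 simulated cohorts. Entries are the chance that all affected patients are called responders.

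| Mean ratio | SD 0.20 | SD 0.30 | SD 0.40 |
|---|---|---|---|
| 0.45 | 93% | 81% | 66% |
| 0.50 | 49% | 45% | 37% |
| 0.55 | 6% | 13% | 14% |

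Near a halving of migraine days, the direction is close to a toss-up for the whole group.

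**Reach.** For k affected patients added to 21 + 21, all k join one class, and k/2 labels are wrong in expectation at p = 50%:

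- k = 2: 2/44 = 4.5% of labels imputed, about 1 wrong.
- k = 8 (ceiling: 15% of 50 = 7.5, rounded up): split 29/21 or 21/29, 8/50 = 16% of labels imputed, about 4 wrong.

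**The case against.** **The affected group is probably very small.** This stands. A patient must have fewer than 10 diary days in each of two months. All have just kept at least 80% of their run-in diary, compliance is watched daily with prompt contact, and compliant months are paid. The 15% in Sample Size is an allowance for any incomplete dataset, including motion and abnormal MRI. A reader might infer that seven or eight labels would be arbitrary; the documents give no count of patients without post-dose diary, so that inference is not supported.

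**Not every dropout is caught.** This also stands. A reader might infer that all withdrawals share one label. A patient who leaves around the week-4 visit has an observed first month, and that score carries individual information into weeks 5-8. With M2/M1 = 0.9 and B = 12, a first-month score of 4 gives 4 × 0.9/12 − 1 = −70%, and 8 gives −40%.

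**Half right is what any single label would give at a 50% response rate.** True, and counting everyone as a non-responder shares that property. The defect is that the rule presents a label without individual information as a derived outcome, in a direction set by the rest of the cohort.

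**Entry into Aim 2 is inferred.** Sample Size counts about 42 full datasets as adequate for the modelling, which leans towards complete cases, and keeping data collected before withdrawal is not the same as extrapolating it. However, the diary section builds the imputation for this end point and for early withdrawal, and nothing excludes the result. If complete cases are intended, the plan should say so.

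**The effect is modest.** With 43 patients, one wrong label moves measured accuracy by at most 1/43 = 2.3 points. The sampling half-width at an assumed accuracy of 75% with 42 patients is 1.96 × √(0.75 × 0.25/42) = 13 points. That limits the harm from one or two patients, though it is no reason to keep labels known to be uninformative.

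**Conclusion.** The point holds for patients with fewer than 10 diary days in both post-dose months. They share one imputed percent change and one responder label that reflects none of their own post-dose data. At about 50% responders the label is right for about half of them, and as written it can enter Aim 2 training and scoring.

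The shared label rests on chaining the rule from run-in. Entry into Aim 2 rests on the plain reading of the diary section and Analysis Plans, not on an explicit sentence. The number affected is unknown, is at most 7 to 8 of 50, and is probably much smaller.

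A reader might also infer that the primary Aim 1 result is compromised. The documents do not support that: the comparison of activation before and after treatment needs a post-treatment scan, which most of these patients would lack. This should be corrected, but it does not threaten the study.

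**What to change.** In the Daily Headache Diary section, keep prorating and the 10-19 day rule. State that no responder label is derived by the cohort-ratio rule for patients with fewer than 10 diary days in both weeks 1-4 and weeks 5-8. For these patients, keep that rule for summaries of mean migraine days only.

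In the Analysis Plans, state the Aim 2 analysis set and leave these patients out of training and scoring. Add two sensitivity analyses:

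- (a) count these patients as non-responders;
- (b) also leave out patients whose weeks 5-8 score alone was imputed from an observed first month.

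Make the change before any labels are derived. The cost is wording and perhaps a few patients fewer in Aim 2, within the allowance already made in Sample Size. Exclusion can itself bias the results if dropout depends on outcome, which is why (a) is needed.

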### Imaging Data Plans

All imaging will be collected at Mayo Hospital on a 3-Tesla Siemens (Siemens MAGNETOM Skyra, Erlangen, Germany) scanner using a 20-channel head/neck coil. Structural analyses will utilize *FreeSurfer* 5.3

(<http://surfer.nmr.mgh.harvard.edu>) a commonly used brain segmentation software for measurements of 68 regional volumes, 68 measurements of cortical thickness, and 68 measurements of cortical surface area. The methodology for FreeSurfer is well-documented and established and includes skull stripping, automated Talairach transformation, segmentation of gray and white matter regions, intensity normalization, brain boundary tessellation, topology correction and deformation of surface structures.(28-32) Resting state (rs)-fMRI data will be analyzed using SPM 8

MRI Sequences		
Siemens Skyra 3T MRI	Technical Details	Acquisition Time
T1 3D MPRAGE	FOV: 256x256 mm  ; Thickness: 1.25 mm; TR:2400 ms; TE:3.03 ms; Voxel size: 1.x1.x1.3 mm 	5.35 min
T2 Turbo Spin Echo	FOV: 256x256 mm  ; Thickness: 4 mm; TR:6800 ms; TE:84 ms; Voxel size: 1.x1.x4 mm 	3.08 min
DTI	FOV: 220x220 mm  ; Thickness: 4 mm; TR:5100 ms; TE:71 ms; Voxel size: 1.7x1.7x4 mm  ; 60 directions	5.33 min
Arterial Spin Labeling (ASL)	FOV: 64x62mm  ; Thickness: 5mm; TR:4600 ms; TE: 22 ms; Voxel Size: 1.7x1.7x5 mm 	5.09 min
BOLD Resting-State	FOV: 256x256 mm  ; Thickness: 4 mm; TR:2500 ms; TE:27 ms; Voxel size: 4.x4.x4 mm 	10.00 min
Event-Related fMRI	FOV: 256x256 mm  ; Thickness: 4 mm; TR:2500 ms; TE:27 ms; Voxel size: 4.x4.x4 mm 	26.60 min
		Total: 55.45 min

(Wellcome Department of Cognitive Neurology, Institute of Neurology, London, UK) and the toolbox DPARSF interfaced with MATLAB version 11.0 (MathWorks, Natick, Ma, USA).(33) Rs-fMRI data will be pre-processed using standard procedures including the following steps: slice-time correction, motion correction, re-alignment, skull and non-brain tissue removal, spatial smoothing, and alignment to an average Montreal Neurological Institute (MNI-305) template.(34, 35) Further post-processing steps will include band-pass filtering, as well as removal of variance related to head motion, white matter signal and cerebrospinal fluid signal. Functional measurements will be imported into SPSS 21.0 (SPSS Inc, Chicago, IL) for further calculations. A region-of-interest approach will be utilized for functional connectivity analyses. The functional connectivity of 33 regions which commonly participate in pain-processing will be analyzed. Event-related BOLD data will be analyzed using a whole-brain analysis, comparing BOLD amplitude during painful stimuli vs. no stimuli. All preprocessing and general linear model (GLM) estimation of brain activation patterns for the event-related portion of the fMRI will also be performed using SPM8, interfaced with Matlab. Functional images will be realigned to the mean volume in the series, motion-corrected, realigned to each individual's structural images, normalized to standard stereotaxic space (Montreal Neurological Institute template) and smoothed using a 5 mm full width half maximum Gaussian kernel. Brain regions activated in response to painful stimuli will be identified by generating contrast maps representing brain activations associated with painful stimuli preceded by auditory cue vs. auditory cue with no painful stimuli. The BOLD signal will be modeled for each of eight successive MR frames (20 seconds) following stimulus presentation, with no assumption made about the shape of the hemodynamic response function. These contrast maps are entered into a mixed effects analysis. A main effects analysis will identify brain regions activated in subjects and a two-sample analysis will identify regions differentially activated when comparing subject cohorts. Cluster threshold correction and multiple comparisons correction will be utilized. 18 major fiber tracts will be reconstructed from DTI data using an automated technique based upon global probabilistic tractography (TRACULA).(36) This software toolbox is available online (<http://surfer.nmr.mgh.harvard.edu/>) and uses anatomical priors (T1-weighted data) as input. The robustness of the TRACULA software algorithm has been validated in prior papers.(36, 37) For each of the 18 fibertracts, tract volume, path length, axial diffusivity, radial diffusivity, mean diffusivity, and fractional anisotropy will be calculated. Arterial Spin Labeling data will be analyzed using SPM 8 and the toolbox ASLtbx.(38) SPM 8 and ASLtbx are freely downloadable online and will be interfaced with MATLAB version 11.0. ASL data will be preprocessed using standard SPM preprocessing steps including orientation resetting, image reorienting, motion correction, and co-registration (of each subjects' T1-weighted image with the ASL images) and data smoothing. Subsequent data post-processing steps will be conducted using the ASLtbx toolbox. Statistical analyses will be conducted using a GLM design.

**Quality control of structural and functional imaging data:** Radiology technicians at Mayo Clinic are already expert with the scanning paradigm and are trained to quality-check images during the MRI. Immediately after imaging is completed, all scans will be checked for motion artifacts. If necessary, patients will be re-scanned on the sequence where excessive motion was detected to ensure proper image quality in each individual. All image post-processing will be conducted on a single Mac workstation running OSX Lion 10.7.5 software to avoid post-processing irregularities related to the use of multiple workstations. All structural brain segmentations and parcellations will be reviewed by a trained technician for data quality. DTI and rs-fMRI data are very sensitive to movement artifacts. Therefore, we will exclude patients that exceed 2 degrees rotational, and/or 2mm translational movement, which are well-recognized cut-off points for movement.(39, 40)

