## **Specific Aims**

- 1. Identify changes in brain function and structure that correlate with response to erenumab.** The objective of this aim is to investigate effects of treatment with erenumab on brain function and structure in patients who respond to treatment with erenumab and in patients who do not respond to treatment with erenumab. Specifically, this aim will assess changes in brain structure (cortical thickness, volume, area, white matter integrity), brain perfusion, resting-state functional connectivity, and pain-induced brain activation patterns in treatment responders and in treatment non-responders. This aim will identify structural and functional brain biomarkers for treatment response with erenumab.
- 2. Develop models to predict which patients will respond to erenumab.** The goal of this aim is to identify structural and functional brain magnetic resonance imaging predictors of response to erenumab in patients with migraine. Specifically, this aim seeks to identify those migraine patients who are going to have a positive response to erenumab treatment versus those who will not respond to treatment. Pre-treatment and early post-treatment imaging data will be used separately, and also in combination, for predictive modeling.

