### Imaging Protocol

Brain MRI will be performed on a Siemens 3T scanner at the Mayo Clinic. The MRI paradigm will include: 1) high-resolution T1-weighted imaging allowing for advanced structural analyses such as determining regional volumes, cortical thickness and surface area; 2) T2-weighted imaging to rule out pre-existing structural brain abnormalities (e.g. incidental findings); 3) Diffusion Tensor Imaging (DTI) used for assessing white matter integrity; 4) ten minutes of resting-state Blood Oxygen Level Dependent (BOLD) signal collection for resting state functional connectivity analyses; 5) event-related paradigm during which patients are exposed to cutaneous thermal stimuli causing moderately intense heat pain so that brain responses to pain can be measured; and 6) Arterial Spin Labeling (ASL) to assess cerebral blood flow.

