#### MRI Stimulations

During the MRI the thermode will be placed on your left forearm. For part of the MRI we will be running 3 different tests during which the thermode will heat up. Each test will last approximately 9 minutes. During each of these tests you will hear a bell and then the thermode temperature may change to a pre-programmed temperature. If so, it will hold at that temperature for 7.5 seconds and then return to baseline. This will be repeated 9 times during each test. You do not need to respond in any way during the tests.

MRI – RAMP & HOLD – temps programmed		
Painful	Non-painful	No stimulus

BOLD STIMULATION #1								
Sequence								
Temp.								
Secs before test								
MRI Frame								

BOLD STIMULATION #2								
Sequence								
Temp.								
Secs before test								
MRI Frame								

BOLD STIMULATION #3								
Sequence								
Temp.								

Secs before test								
MRI Frame								

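### Motion re-scans are tied to the end of imaging and no scan order is fixed, so a repeated resting-state scan, and possibly perfusion, could be acquired after the heat runs

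*Combined protocol and SAP*

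**What the plan says.** Three places bear on the order in which scans are taken.

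- **Imaging Data Plans, quality-control paragraph.** Technicians are "trained to quality-check images during the MRI". Then: "Immediately after imaging is completed, all scans will be checked for motion artifacts. If necessary, patients will be re-scanned on the sequence" in which motion was found. The paragraph names diffusion and resting-state data as very sensitive to movement and sets exclusion limits of 2 degrees and 2 mm. It gives no timing for a repeat, no same-day or other-day rule, no interval after the heat runs, and no flag for repeated data.
- **Imaging Protocol.** The text numbers the sequences. Resting-state comes directly before heat: "4) ten minutes of resting-state Blood Oxygen Level Dependent (BOLD) signal collection for resting state functional connectivity analyses; 5) event-related paradigm". The list ends "and 6) Arterial Spin Labeling (ASL) to assess cerebral blood flow", which puts perfusion after the heat paradigm.
- **MRI Sequences table.** The rows run T1, T2, DTI, ASL, resting-state, event-related fMRI. Perfusion is here listed before both the resting-state and the heat runs.

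The MRI Stimulations form in the Appendix describes three heat tests of about 9 minutes each. Of the trials within a test it says "This will be repeated 9 times during each test". Trials are painful, non-painful or without stimulus, and each hold lasts 7.5 seconds.

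The Aim 1 measures include "brain perfusion, resting-state functional connectivity, and pain-induced brain activation patterns". Analysis Plans makes pain-induced activation the primary analysis and describes the other measures as explored. Table 1 schedules imaging at baseline, week 2 and week 8.

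**The concern.** Resting-state connectivity is to be analysed in 33 regions that commonly take part in pain processing. These are the regions one would least want to scan just after noxious heat. If a resting-state run fails the motion check and is repeated at the end of the session, the replacement is taken in a different state from the scan it replaces. If repeats are more common at one visit than another, part of the pre- to post-treatment change reflects scan order.

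For perfusion, the position relative to heat depends on which list the site follows. A fixed position at every visit would keep the comparison like with like in timing. A position after heat would still leave perfusion open to carry-over from a pain response that treatment may itself alter.

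The heat sequence has a smaller version of the same problem. A repeat of the whole event-related sequence follows a complete heat session, and this sequence supplies the primary outcome. A baseline scan taken in the wrong state cannot be acquired again once treatment has begun.

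**Working it through.** **1. Reproduce the plan's session time.** The MRI Sequences table gives 5.35 + 3.08 + 5.33 + 5.09 + 10.00 + 26.60 = 55.45 min, which matches the stated total. The Stimulations form agrees: 3 × about 9 min = about 27 min, against 26.60 min in the table (26.60 / 3 = 8.87 min per run).

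**2. How much of the heat block is heat.**
- Trials: 3 runs × 9 = 27.
- Upper bound on hold time, if every trial delivered heat: 27 × 7.5 s = 202.5 s = 3.4 min.
- Share of the block: 202.5 / (26.60 × 60) = 202.5 / 1596 = 13%.
- The split between trial types is not stated. If the three types were equally frequent (an assumption), painful hold would be 9 × 7.5 s = 67.5 s = 1.1 min, and heat of any kind 135 s = 2.25 min.
- Ramp time is not included.

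**3. Where each scan falls under each list, read as a running order.**

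| | Imaging Protocol list | MRI Sequences table |
|---|---|---|
| Heat runs start | 5.35 + 3.08 + 5.33 + 10.00 = 23.76 min | 5.35 + 3.08 + 5.33 + 5.09 + 10.00 = 28.85 min |
| Heat runs end | 23.76 + 26.60 = 50.36 min | 28.85 + 26.60 = 55.45 min |
| First-pass resting-state | before heat | before heat |
| First-pass ASL | after heat (from 50.36 min) | before heat |
| Earliest resting-state repeat after the final check | 55.45 min, after all heat runs | 55.45 min, after all heat runs |

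First-pass resting-state is safe under both lists, and only its repeats are affected. ASL goes from always after heat to never after heat on first pass, depending on the list.

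**4. What a heat repeat involves.** The re-scan rule works by sequence, and the event-related sequence is one 26.60-minute entry in the table. Repeating a single failed run would take about 8.87 min.

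**5. Carry-over.** The documents give neither a repeat rate nor a size for any after-effect of heat, so no bias can be computed from them.

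**The case against.** The strongest reply is that the plan already has an in-session check. The sentence before the quoted rule says technicians look at image quality during the MRI, so a failed resting-state run might be repeated before heat begins. This stands in part. The plan does not say that checks or repeats happen only at the end, and a reader who infers that goes beyond the text. But the in-session check is not said to trigger a repeat, whereas the check after imaging is.

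Neither list claims to be a running order. One says what the paradigm includes and the other is a table of technical parameters. That also stands: the two differ in order without strictly contradicting each other, and the gap is that no order is fixed. That a repeat takes place in the same session is likewise inferred.

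Four stronger readings should be resisted.

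- **About 27 minutes of continuous heat pain.** That figure is run time. Step 2 bounds the heat hold at 3.4 min.
- **A stated false-positive rate.** Suppose repeats shift a measure by s standard deviations of within-patient change and the share repeated differs by q between visits. With 21 patients and a two-sided 5% t-test, the noncentrality is s × q × √21. Values of s × q of 0.10, 0.20 and 0.30 give 7.2%, 14.1% and 25.8%. With s up to 1, the rate stays near 5% when q is 0.05 or less. Both s and q are invented, and the calculation ignores the multiple-comparison correction planned for the event-related data.
- **Damage to the power statement.** The 88% in Sample Size does not depend on this point; a two-sample t-test with 21 per group and a standardised difference of 1 gives 88.5%.
- **An ASL scan that cannot cover the brain.** The 64 × 62 mm field of view looks like a table-entry error beside 220 to 256 mm for the other sequences. It has no bearing on scan order.

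The thermal testing form also leads on to the MRI instructions, so first-pass resting scans may follow some heat pain too. Reordering the scans would not remove that.

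**Conclusion.** The point holds as a gap in specification. The stated re-scan rule is tied to the end of imaging, so a resting-state repeat in the same session follows the heat runs under either list. First-pass ASL may or may not follow them, because no order is fixed. The exposure is 26.60 min of intermittent runs with at most 3.4 min of heat hold, only part of it painful.

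This conclusion assumes that repeats are made in the same session, that the final check is what prompts them, and, for ASL, that a site might run the Imaging Protocol list as written. The effect on results cannot be sized from the documents. Connectivity and perfusion are exploratory; the primary outcome is touched only where a heat sequence is repeated. This is a worthwhile, inexpensive improvement and does not undermine the primary analysis.

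**What to change.** - **Quality-control paragraph:** check motion at the end of each sequence, before the next begins, and repeat any failed resting-state or ASL scan before the first heat run. Check each heat run as it ends and repeat only the run that failed.
- **Imaging Protocol and MRI Sequences table:** state one running order for all three imaging visits, with ASL and resting-state before heat, and make the two lists agree.
- **Analysis Plans:** flag any resting-state or ASL scan, or heat run, acquired out of that order, and report a sensitivity analysis without the flagged scans. Outright exclusion is harder to defend, because it would remove data from the patients who move most when only about 21 per group are expected.
- **Separately, as a clerical matter:** correct the ASL field-of-view entry in the table.

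The cost is protocol wording, a scan-card order and a short pause for checking between sequences. A resting-state or ASL repeat takes the same scanner time before heat as after it, and repeating one heat run is shorter than repeating all three. A repeated heat run will still follow earlier heat runs, which is why it is flagged.
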